7.3.4 GI Symptoms – patients greater or equal to 10 years old

The GI symptom questionnaire consists of 6 items, 5 of which are scored using a 0 – 10 rating scale with item appropriate end anchors to rate the symptom, for example Pain in your belly 0 = no pain and 10 = worst pain, with the numbers 1-9 labeled in between. The sixth item assesses bowel movement frequency during the past 24 hours, using 7 response options 0 = 0 (none), 1 = 1, 2 = 2, 3 = 3, 4 = 4, 5 = 5 – 10 and 6 = 11 or more.

A GI summary score will be created using the 10 point response scale items (5 items), Item 6 will be excluded from the calculation of the GI symptom summary score and used in the analysis as a standalone item. Overall, higher scores on the GI symptom diary items and the summary score will indicate worse symptoms.

Weekly GI diary symptoms summary scores as well as item 6 (bowel movement) will be summarized using descriptive statistics at Screening, week 4, week 24, week 28 and week 48.

7.3.5 Observer Reported GI Symptoms – patients less than 10 years old

An observer GI symptoms questionnaire will be administered to those patients who are 2-9 years old. All items will be completed by the parents of the patients. All items are the same and the scoring algorithm remains the same.

Weekly GI diary symptoms summary scores as well as item 6 (bowel movement) will be summarized using descriptive statistics at Screening, week 4, week 24, week 28 and week 48.

7.3.6 Palatability – patients greater or equal to 10 years old

The palatability questionnaire consists of 4 items. Two items measure the taste and aftertaste of the medication and are scored on a 5 point response scale with the response format 1 “Very good”, 2 “Good”, 3 “Neither good nor bad”, 4 “Bad” and 5 “Very bad”. The aftertaste item offers an additional response option of “no aftertaste”. This response option will be recoded such that all patients have a response, for example, patients who choose this option will be coded 0 and patients who rated the aftertaste will be coded 1. This will result in binary (yes/no) aftertaste item.

The remaining palatability items refer to whether the medication was taken (i.e., swallowed or vomited) and how the patient perceived the amount of medication to be taken.

A summary of Items 1, 3 and 4 leading to the palatability summary score will be constructed using the following rules:

Recode Item 1 “Very good”, “Good” & “Not good or bad” =1

“Bad” & “Very bad” = 2

Recode Item 2 “Swallowed ALL of the medicine” =1

“Spat out SOME of the medicine” & “Spat out ALL of the medicine” & “Swallowed none” =2

“Vomited within 30 minutes after swallowing the medicine” = 3

Recode Item 3 “Not enough liquid” & “Too much liquid” = 1

“Just enough liquid” = 2

No missing data will be imputed when calculating the palatability summary score.

The [Table 7-5](#) presents the Items 1, 3 and 4 scoring matrix leading to the palatability summary score:

Table 7-5 Scoring Matrix

Palatability Score	Item1 – taste	Item3 – what happened	Item4 – amount	Definition
0	Bad & Very bad; 2	Vomited < 30 min; 3	Not enough & too much; 1	Worst palatability
1	Bad & Very bad; 2	Vomited < 30 min; 3	Just enough: 2	1
2	Bad & Very bad; 2	Spat some/ all out; 2	Not enough & too much; 1	2
3	Bad & Very bad; 2	Spat some/ all out; 2	Just enough: 2	3
4	Bad & Very bad; 2	Swallowed all: 1	Just enough: 2	4
5	Bad & Very bad; 2	Swallowed all: 1	Not enough & too much; 1	5
6	V. good, Good & Not good/bad; 1	Vomited < 30 min; 3	Not enough & too much; 1	6
7	V. good, Good & Not good/bad; 1	Vomited < 30 min; 3	Just enough: 2	7
8	V. good, Good & Not good/bad; 1	Spat some/ all out; 2	Not enough & too much; 1	8
9	V. good, Good & Not good/bad; 1	Spat some/ all out; 2	Just enough: 2	9
10	V. good, Good & Not good/bad; 1	Swallowed all: 1	Not enough & too much; 1	10
11	V. good, Good & Not good/bad; 1	Swallowed all: 1	Just enough: 2	Best palatability

The palatability summary score will be summarized using descriptive statistics by treatment arm and week (Screening, week 4, week 24, week 28 and week 48).

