7.3.7 Observer Reported Palatability – patients less than 10 years old

An observer palatability questionnaire will be administered to those patients who are 2-9 years old. All items will be completed by the parents of the patients. All items are the same and the scoring algorithm remains the same as outlined in [Section 7.3.6](#).

The palatability summary score will be summarized using descriptive statistics by treatment arm and week (Screening, week 4, week 24, week 28 and week 48).

8 Safety monitoring and reporting

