### **Palatability using PRO/ ObsRO questionnaire**

The palatability questionnaire consists of 4 items. Two items measure the taste and aftertaste of the medication and are scored on a 5 point response scale. The remaining palatability items refer to whether the medication was taken (i.e. swallowed or vomited) and how the patient perceived the amount of medication to be taken.

For the palatability questionnaire the overall score will be constructed using a scoring matrix from the score of items. Standard descriptive analyses including absolute and relative changes will be performed for both formulations (DT/FCT) for the overall score at Week 4, Week 24, Week 28 and Week 48 and overall score at Screening for iron chelators. The baseline data for treatment period 1 and 2 will be Week 4 and Week 24 data respectively, only one assessment is observed at Screening period. The summary will be provided separately for PRO and ObsRO patient groups.

The standard descriptive analyses include: n, mean, standard deviation, minimum, median and maximum. The 95% CI for the absolute and relative (or difference) change from baseline of the overall score will also be presented for the treatments.

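### In Protocol Table 7-5 the palatability scores 4 and 5 break the scale's own order: with bad taste and the dose fully swallowed, the right amount scores below the wrong amount.

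*Protocol*

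**What the plan says.** Protocol 7.3.6 builds the palatability summary score from taste (Item 1), what happened to the dose (Item 3) and the perceived amount (Item 4). Each answer is recoded and Table 7-5 then assigns a score. Score 0 is labelled "Worst palatability" and score 11 "Best palatability".

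The two rows at issue are:

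- score 4: "Bad & Very bad; 2 Swallowed all: 1 Just enough: 2 4"
- score 5: "Bad & Very bad; 2 Swallowed all: 1 Not enough & too much; 1 5"

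The rows just above them, for bad taste with some or all spat out, run the other way. The just-enough row takes the higher score: "Bad & Very bad; 2 Spat some/ all out; 2 Just enough: 2 3".

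Protocol 7.3.7 applies the same scoring to observer reports for children aged 2 to 9: "All items are the same and the scoring algorithm remains the same". Protocol 10.5.6 leaves scoring details to the SAP. SAP 2.11 says only that "the overall score will be constructed using a scoring matrix from the score of items". It does not reproduce the matrix, and SAP Section 4 (changes to protocol-specified analyses) reads as not applicable. SAP Section 1 makes the protocol's conventions the default, so Table 7-5 is the operative rule.

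**The concern.** A scale that runs from worst to best should never give a lower score to a response that is at least as good on every item. Table 7-5 does so once. A patient who dislikes the taste but swallows everything scores better if the amount was wrong than if it was right.

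Palatability under FCT, DT and previous chelation is a named secondary objective (Protocol Table 3-1, SAP Table 1.2.1). It is summarised as absolute and relative change with 95% confidence intervals. A patient in this pair who moves from a wrong amount to the right amount is recorded as worsening. The error in a group mean cancels between formulations only if the balance of the two rows is the same under both. That cannot be assumed. The amount answers are worded in terms of liquid, and DT is dispersed in a glass of liquid while FCT is swallowed whole or crushed onto soft food (Protocol 6.1.1).

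A smaller defect sits beside it. The recode list, introduced as "leading to the palatability summary score will be constructed using the following rules", labels the swallowing and amount answers Items 2 and 3. The sentence introducing it and the matrix use Items 3 and 4.

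**Working it through.** **Inputs.** All twelve rows of Table 7-5 with their printed codes: taste (2 = bad, 1 = not bad), what happened (3 = vomited, 2 = spat out, 1 = swallowed all), amount (1 = not enough or too much, 2 = just enough). In both suspect rows the label agrees with its code and the definition column repeats the score, so a text-extraction error is unlikely.

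**Step 1: compare within pairs.** Taste and outcome are held fixed.

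| Taste | What happened | Wrong amount | Just enough | Difference |
|---|---|---|---|---|
| Bad | Vomited | 0 | 1 | +1 |
| Bad | Spat out | 2 | 3 | +1 |
| Bad | Swallowed all | 5 | 4 | **−1** |
| Not bad | Vomited | 6 | 7 | +1 |
| Not bad | Spat out | 8 | 9 | +1 |
| Not bad | Swallowed all | 10 | 11 | +1 |

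The matching pair with better taste (10 and 11) runs the expected way, so full swallowing does not explain the exception.

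**Step 2: fit the ordering the table implies.** Let T = 1 if taste is not bad and 0 if bad, H = the what-happened code, and A = the amount code. Then

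score = 6 × T + 2 × (3 − H) + (A − 1).

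This reproduces 10 of the 12 printed scores. The two misses are:

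- bad, swallowed all, just enough: 0 + 2 × 2 + 1 = 5, printed 4
- bad, swallowed all, wrong amount: 0 + 2 × 2 + 0 = 4, printed 5

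A search over all pairs of rows for a response at least as good on every item but scored lower finds exactly one case, this one. Swapping the two scores removes it, and all twelve rows then fit.

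**Step 3: effect on one patient.** Each response in these rows is off by 1 point. A move from wrong amount to just enough is recorded as 4 − 5 = −1. The table's ordering gives 5 − 4 = +1, a discrepancy of 2 points.

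**Step 4: effect on a group mean.** Let w be the share of scored responses in the wrong-amount row and j the share in the just-enough row. The printed score is 1 too high in the first and 1 too low in the second, so

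error in the mean = w − j.

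The documents give neither share. The values below are assumptions that show the range of behaviour.

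| j (just enough) | w (wrong amount) | Error w − j |
|---|---|---|
| 20% | 5% | −0.15 |
| 30% | 10% | −0.20 |
| 10% | 10% | 0 |
| 5% | 20% | +0.15 |

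**Step 5: effect on the FCT–DT difference.** The error is (w − j for FCT) minus (w − j for DT). On the assumed shares above:

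- DT at j = 20%, w = 5% and FCT at 10% each: 0 − (−0.15) = +0.15
- DT at j = 5%, w = 20% and FCT at 10% each: 0 − 0.15 = −0.15
- the same balance under both: 0

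**The case against.** The strongest reply is that the rows are only inferred to be reversed. The instrument's scoring source is not in the documents, and Protocol 2.2 describes the questionnaires as validated. An intended exception cannot be excluded. This stands, and it is why the fix starts with a check of the source. It does not remove the point, because an unexplained break in a worst-to-best scale has to be either corrected or justified.

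A second reply is that the consequence is small. SAP 2.7.2 states that secondary endpoints carry no formal hypothesis testing, and palatability receives only descriptive summaries and confidence intervals. The comparison with previous chelation is also narrower than it looks. Chelation-naïve patients, those without chelation in the six months before screening and those previously on deferoxamine need not complete the screening palatability questionnaire (footnotes to Protocol Table 7-1). All of this stands and limits the weight of the point.

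A third reply is that the item mislabelling is editorial. This largely stands. Each recode line carries its response text, and the codes match the matrix columns, so the intended mapping can be recovered.

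A reader might also infer that the matrix inflates FCT's advantage, on the argument that bad taste with full swallowing is commoner on DT and mostly paired with a just-enough answer. The documents do not support that. They report no cell frequencies, and Step 5 shows that the sign depends on which row predominates under each formulation.

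**Conclusion.** The point holds. As printed, Table 7-5 is not monotone: one of six pairs ranks the right amount below the wrong amount, no text explains it, and the SAP carries it forward for both patient and observer scores. Each response in the two rows is off by 1 point on a 0–11 scale, measured against the table's own ordering. A mean is off by w − j, which cannot exceed the combined share of the two rows. The direction and size of any error in the FCT–DT comparison are unknown, and it may be zero.

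This rests on one assumption: that the ordering followed by the other ten rows is the intended one. The primary preference analysis, its power and its error rate are unaffected. A reader should not conclude that the palatability results are unusable, because the item responses are recorded and the score can be re-derived.

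**What to change.** 1. Check the order of scores 4 and 5 against the instrument's source scoring. Unless the source justifies the exception, score bad taste, swallowed all, not enough or too much as 4, and bad taste, swallowed all, just enough as 5. If the exception is intended, state the reason.
2. Print the final matrix in SAP 2.11, with the recode rules labelled Items 1, 3 and 4, and apply it to both patient and observer data.
3. Record the change in SAP Section 4 in place of the not-applicable entry.
4. Label it a post-lock scoring correction and show palatability results under both scorings. The SAP document history has an entry dated 8 April 2021, after the interim database lock. That interim follows completion of Week 48 by all patients (SAP 2.14), and Week 48 is the last scheduled palatability assessment (Protocol Table 7-1).

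The cost is a small amount of documentation, re-derivation and a second set of palatability tables, with no new data. If the sponsor also wants to change the protocol's own table, Protocol 12.1 requires a written amendment.

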7.3.7 Observer Reported Palatability – patients less than 10 years old

An observer palatability questionnaire will be administered to those patients who are 2-9 years old. All items will be completed by the parents of the patients. All items are the same and the scoring algorithm remains the same as outlined in [Section 7.3.6](#).

The palatability summary score will be summarized using descriptive statistics by treatment arm and week (Screening, week 4, week 24, week 28 and week 48).

8 Safety monitoring and reporting

8.1 Adverse events

8.1.1 Definitions and reporting

An adverse event is defined as the appearance of (or worsening of any pre-existing) undesirable sign(s), symptom(s), or medical condition(s) that occur after patient's signed informed consent has been obtained.

Abnormal laboratory values or test results occurring after informed consent constitute adverse events only if they induce clinical signs or symptoms, are considered clinically significant, require therapy (e.g., hematologic abnormality that requires transfusion or hematological stem cell support), or require changes in study medication(s).

Except for screening failures, adverse events that begin or worsen after informed consent should be recorded in the Adverse Events eCRF. Conditions that were already present at the time of informed consent should be recorded in the Relevant Medical History/Current Medical Conditions eCRF page. Adverse event monitoring should be continued for at least 30 days (or 5 half-lives, whichever is longer) following the last dose of study treatment. Adverse events (including lab abnormalities that constitute AEs) should be described using a diagnosis whenever possible, rather than individual underlying signs and symptoms. When a clear diagnosis cannot be identified, each sign or symptom should be reported as a separate Adverse Event.

Severity of adverse events will be assessed as mild, moderate, or severe. Information about deaths will be collected through an SEC form.

The occurrence of adverse events should be sought by non-directive questioning of the patient during the screening process after signing informed consent and at each visit during the study. Adverse events also may be detected when they are volunteered by the patient during the screening process or between visits, or through physical examination, laboratory test, or other assessments. As far as possible, each adverse event should be evaluated to determine:

1. The severity grade (mild, moderate, or severe)
2. Its duration (Start and end dates or Ongoing at End of Study)
3. Its relationship to the study treatment (Reasonable possibility that AE is related: suspected vs non-suspected)
4. Action taken with respect to study or investigational treatment (none, dose adjusted, temporarily interrupted, permanently discontinued, unknown, not applicable)
5. Whether medication or therapy was given (no concomitant medication/non-drug therapy, concomitant medication/non-drug therapy)
6. Whether it is serious, where a serious adverse event (SAE) is defined as in [Section 8.2.1](#)

All adverse events should be treated appropriately. If a concomitant medication or non-drug therapy is given, this action should be recorded on the Adverse Event eCRF.

Once an adverse event is detected, it should be followed until its resolution or until it is judged to be permanent, and assessment should be made at each visit (or more frequently, if necessary)

of any changes in severity, the suspected relationship to the study treatment, the interventions required to treat it, and the outcome.

8.1.2 Laboratory test abnormalities

8.1.2.1 Definitions and reporting

Laboratory abnormalities that constitute an Adverse event in their own right (are considered clinically significant by investigator, induce clinical signs or symptoms, require concomitant therapy or require changes in study treatment), should be recorded on the Adverse Events eCRF. Whenever possible, a diagnosis, rather than a symptom should be provided (e.g. anemia instead of low hemoglobin). Laboratory abnormalities that meet the criteria for Adverse Events should be followed until they have returned to normal or an adequate explanation of the abnormality is found. When an abnormal laboratory or test result corresponds to a sign/symptom of an already reported adverse event, it is not necessary to separately record the lab/test result as an additional event.

Laboratory abnormalities, that do not meet the definition of an adverse event, should not be reported as adverse events. A severe event does not automatically indicate a SAE unless it meets the definition of serious as defined below and/or as per investigator's discretion. A dose hold or medication for the lab abnormality may be required by the protocol in which case the lab abnormality would still, by definition, be an adverse event and must be reported as such.

8.2 Serious adverse events

8.2.1 Definitions

Serious adverse event (SAE) is defined as one of the following:

- Is fatal or life-threatening
- Results in persistent or significant disability/incapacity
- Constitutes a congenital anomaly/birth defect
- Is medically significant, i.e., defined as an event that jeopardizes the patient or may require medical or surgical intervention to prevent one of the outcomes listed above
- Requires inpatient hospitalization or prolongation of existing hospitalization,
 - Note that hospitalizations for the following reasons should not be reported as serious adverse events:
- Routine treatment or monitoring of the studied indication, not associated with any deterioration in condition
- Elective or pre-planned treatment for a pre-existing condition that is unrelated to the indication under study and has not worsened since signing the informed consent
- Social reasons and respite care in the absence of any deterioration in the patient's general condition
- Note that treatment on an emergency outpatient basis that does not result in hospital admission and involves an event not fulfilling any of the definitions of a SAE given above is not a serious adverse event

8.2.2 Reporting

To ensure patient safety, every SAE, regardless of suspected causality, occurring after the patient has provided informed consent and until at least 30 days after the patient has stopped study treatment must be reported to Novartis within 24 hours of learning of its occurrence.

Any SAEs experienced after this 30 days period should only be reported to Novartis if the investigator suspects a causal relationship to the study treatment. Recurrent episodes, complications, or progression of the initial SAE must be reported as follow-up to the original episode within 24 hours of the investigator receiving the follow-up information. An SAE occurring at a different time interval or otherwise considered completely unrelated to a previously reported one should be reported separately as a new event.

Information about all SAEs is collected and recorded on the Serious Adverse Event Report Form; all applicable sections of the form must be completed in order to provide a clinically thorough report. The investigator must assess and record the relationship of each SAE to each specific study treatment (if there is more than one study treatment), complete the SAE Report Form in English, and send the completed, signed form by fax within 24 hours to the oncology Novartis Drug Safety and Epidemiology (DS&E) department.

The telephone and telefax number of the contact persons in the local department of Drug Safety and Epidemiology (DS&E), specific to the site, are listed in the investigator folder provided to each site. The original copy of the SAE Report Form and the fax confirmation sheet must be kept with the case report form documentation at the study site.

Follow-up information is sent to the same contact(s) to whom the original SAE Report Form was sent, using a new SAE Report Form stating that this is a follow-up to the previously reported SAE and giving the date of the original report. Each re-occurrence, complication, or progression of the original event should be reported as a follow-up to that event regardless of when it occurs. The follow-up information should describe whether the event has resolved or continues, if and how it was treated, whether the blind was broken or not, and whether the patient continued or withdrew from study participation.

If the SAE is not previously documented in the Investigator's Brochure or Package Insert (new occurrence) and is thought to be related to the Novartis study treatment, an oncology Novartis Drug Safety and Epidemiology (DS&E) department associate may urgently require further information from the investigator for Health Authority reporting. Novartis may need to issue an Investigator Notification (IN), to inform all investigators involved in any study with the same drug that this SAE has been reported. Suspected Unexpected Serious Adverse Reactions (SUSARs) will be collected and reported to the competent authorities and relevant ethics committees in accordance with Directive 2001/20/EC or as per national regulatory requirements in participating countries.

8.3 Emergency unblinding of treatment assignment

Not applicable, this is an open-label treatment study.

8.4 Pregnancies

To ensure patient safety, each pregnancy occurring while the patient is on study treatment must be reported to Novartis within 24 hours of learning of its occurrence. The pregnancy should be followed up to determine outcome, including spontaneous or voluntary termination, details of the birth, and the presence or absence of any birth defects, congenital abnormalities, or maternal and/or newborn complications.

Pregnancy should be recorded on a Clinical Trial Pregnancy Form and reported by the investigator to the oncology Novartis Drug Safety and Epidemiology Department (DS&E). Pregnancy follow-up should be recorded on the same form and should include an assessment of the possible relationship to the study treatment any pregnancy outcome. Any SAE experienced during pregnancy must be reported on the SAE Report Form.

Pregnancy outcomes must be collected for the female partners of any males who took study treatment in this study. Consent to report information regarding these pregnancy outcomes should be obtained from the mother.

